METHODS: Equal numbers of healthy men and women will be recruited. At least 3 days prior to study subjects will be trained to rate pain in response to heat applied to the lateral calf using a Peltier controlled thermode, and to rate pain in response to 225 mN von Frey filament testing within the area of hypersensitivity induced and maintained by transient application of topical capsaicin followed by intermittent heat (Petersen, 1999).

Subjects will return for study visit two and be randomized into one of 3 groups of 12 subjects each to receive, in a double-blind manner, intrathecal saline or intrathecal oxytocin, 15 µg or 150 µg. The solutions will be prepared and dispensed to this institution under IND approval and regulation from the Food and Drug Administration and will be released to the investigators through the research pharmacy at Wake Forest School of Medicine.

A stimulus response to heat pain will be performed, then intrathecal injection of the study solution in a 3 ml volume will occur via a #27 or #25 Whitacre needle inserted in a lower lumbar interspace. Thirty minutes later capsaicin will be applied to the lateral calf to generate hypersensitivity. Capsaicin will be removed and the area re-kindled 40 min later by application of a thermode at 40°C for 5 minutes. Areas of hyperalgesia and allodynia and, within the area of hyperalgesia, stimulus response to von Frey filament testing, will be determined upon removal of capsaicin and after 3 rekindlings at 40 minute intervals.

We will abandon an individual participant's study and schedule another participant to receive the same randomization, should we be unable to successfully place the intravenous catheter (IV) or the spinal needle to inject the intrathecal oxytocin. In our experience, this occurs in less than 10% of participants. We maintain an extensive listing (IRB approved Database BG 05-468: PI: [name].) of our previous Clinical Research Unit (CRU) volunteers who have requested to be notified by mail or email that they might qualify for participation in another volunteer study. It is from this list and potential volunteers that we maintain that we

anticipate recruitment of most of our volunteers. Should we need to advertise for additional volunteers we will submit a proposed advertising method to the IRB for approval.

STUDY DESIGN

Inclusion Criteria: We request permission to study up to 40 subjects so that we will have 36 evaluable subjects.

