Study Visit 1: The participant will report to the Clinical Research Unit (CRU) at least 3 days prior to study visit 2. The participant will review and sign the Informed Consent. After informed consent is adequately obtained, a detailed medical history will be obtained from the participant, female participants will have blood drawn and sent to the laboratory to determine pregnancy status. The research nurse will train the participants to estimate pain quantitatively using a 2 cm² peltier controlled thermode (TSA®) applied to the forearm. Typically, the participant is exposed to temperatures between 38⁰ and 51⁰ C using a random staircase method.

The participant will also be trained to reproducibly define the limits of hyperalgesia and allodynia on the skin of the lateral calf established by heating the skin to 45°C for 5 minutes, applying topical capsaicin (0.075% cream, Bioglan Pharmaceuticals) under an occlusive dressing for 30 minutes, then heating the application site to 40°C for 5 minutes every 40 minutes (rekindling) as previously described (Petersen, 1999).

During this training period, the participant's blood pressure, heart rate, and peripheral oxyhemoglobin saturation will be recorded. A 12 Lead electrocardiogram (EKG) will also be performed.

We have found this training session significantly reduces anxiety and variability in pain and hypersensitivity ratings on subsequent study days.

Study Visit 2

On the second visit, the participant will report to the CRU, in the morning after having had nothing to eat or drink since midnight. A peripheral intravenous catheter will be inserted into a vein in an upper extremity and lactated Ringers solution infused at 1.5 ml/kg/hr for the duration of the study. After obtaining baseline measures the subject will be placed into a lateral position and one of the investigator physicians will insert a #25 or #27 Whitacre spinal needle in a lumbar interspace using a sterile technique. After obtaining clear, free-flow CSF, a 2 milliliter sample of CSF will be obtained and stored for future use under IRB Protocol: 00003383, the sample will be

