stored with a unique identifier. Oxytocin in a 3 ml volume, diluted with sterile normal saline, or a 3 ml injection of sterile normal saline (placebo) will then be injected over 30 seconds. Oxytocin will be prepared by Med Solutions in Winston Salem, North Carolina and will be shipped to WFUHS for research study purposes only. The spinal needle will be removed and the volunteer placed supine with the head of the bed elevated for the next portion of the study. 30 minutes after the spinal injection the skin on the lateral calf will be heated to 45°C for 5 minutes then topical capsaicin cream will be applied to the lateral calf to generate hypersensitivity and remain on the skin for 30 minutes. Capsaicin will be removed and the area re-kindled 40 min later by application of a thermode at 40°C for 5 min. Areas of hyperalgesia and allodynia and, within the area of hyperalgesia, stimulus response to von Frey filament testing, will be determined upon removal of capsaicin and after 3 re-kindlings at 40 minute intervals. Three blood samples will be obtained after the spinal oxytocin injection at the following intervals: 10, 45, 120 minutes. The blood will be drawn from the existing intravenous catheter that is in place. If the sample cannot be obtained through the intravenous catheter, the sample will be abandoned. The samples are being drawn for the analysis of systemic oxytocin after spinal administration.

Safety and Monitoring:

Assessment of Side Effects: Significant side effects are defined as changes > 30% from baseline in the mean arterial pressure, HR, or oxyhemoglobin pulse oximetry < 90. Any unexpected or serious side effects will be reported to the IRB and the FDA within 24 hrs. Peripheral oxyhemoglobin saturation, BP and HR will be measured non-invasively before and 15, 30, 60, 120, 180, 240, minutes after administering spinal oxytocin and the electrocardiogram will be monitored continuously for the duration of the study.

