Primary outcome measure will be the area of hyperalgesia after the first skin heating following topical capsaicin.

Group comparison: Areas of hyperalgesia after the first skin heating following topical capsaicin will be compared among the three groups using one-way ANOVA.

Power analysis: Based on previously published work by us with this model in which the intrathecal placebo group had an area of hyperalgesia of $62 \pm 12 \text{ cm}^2$, a group size of 12 will allow us to observe a difference among groups of 15 cm^2 with $\alpha=0.05$ and $1-\beta=0.80$. A 25% reduction in area of hyperalgesia is considered by us and other groups to be clinically predictive

of reduction in hyperalgesia and in spontaneous pain in patients with neuropathic pain with the same intervention.

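### The primary ANOVA uses no pre-treatment covariate, although the Visit 1 capsaicin session could supply one if the area of hyperalgesia were recorded there

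*Combined protocol and SAP*

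**What the plan says.** STATISTICAL RATIONALE defines the endpoint: "Primary outcome measure will be the area of hyperalgesia after the first skin heating following topical capsaicin". The analysis follows: "Areas of hyperalgesia after the first skin heating following topical capsaicin will be compared among the three groups using one-way ANOVA". No covariate or baseline adjustment is mentioned there or elsewhere.

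Allocation takes place at the second visit (METHODS): "Subjects will return for study visit two and be randomized into one of 3 groups of 12 subjects each".

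Visit 1 is held at least 3 days earlier. Under Study Visit 1, the calf is heated to 45°C for 5 minutes, capsaicin is applied for 30 minutes, and the site is then rekindled at 40°C for 5 minutes every 40 minutes. In that session, "The participant will also be trained to reproducibly define the limits of hyperalgesia and allodynia on the skin of the lateral calf". The measurements the section says are recorded or performed are vital signs and an electrocardiogram. Recording of the area is not mentioned.

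Under Study Visit 2 the same heating, capsaicin and rekindling steps follow the spinal injection. There the plan does call for measurement: the areas "will be determined upon removal of capsaicin and after 3 re-kindlings at 40 minute intervals". Because capsaicin comes after the injection, Visit 2 cannot provide a pre-treatment area.

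**The concern.** People may differ in how large an area of hyperalgesia capsaicin produces. In an unadjusted ANOVA, any stable part of that difference stays in the error term. With only 12 per group this affects both the power of the F test and the width of the intervals for each dose against saline.

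Visit 1 is the only place in the design where the primary outcome could be observed before treatment. The session, the capsaicin and the mapping training are already planned. What is missing is an instruction to record the area, and an analysis that uses it. Additional precision would otherwise have to come from more volunteers, each with a lumbar puncture.

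**Working it through.** **Inputs.** From STATISTICAL RATIONALE: placebo mean 62 cm², spread 12 cm² (read as an SD), difference 15 cm², alpha 0.05, power 0.80, 12 per group. The correlation r between the Visit 1 and Visit 2 areas is not in the documents. I take r = 0, 0.3, 0.5 and 0.7.

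**The plan's own figure.** An exact two-sided two-sample t test with SD 12 and difference 15 needs 12 per group (power 83.3%; 79.6% at 11 per group). The stated group size reproduces.

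**Unadjusted F test**, df (2, 33), critical value 3.285, λ = 12 × Σ(mean − grand mean)² / 144:

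- Equally spaced means 62/54.5/47: λ = 12 × (7.5² + 0 + 7.5²)/144 = 9.375; power 74.8%.
- One group differs, 62/62/47: λ = 12 × (5² + 5² + 10²)/144 = 12.5; power 86.5%.

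**Adjusted F test**, df (2, 32), critical value 3.295. Residual variance is 144(1 − r²). Chance imbalance in the covariate inflates the variance of group contrasts on average by 1 + 1/(36 − 3 − 2) = 1 + 1/31. So λ_adj = λ / [(1 − r²)(1 + 1/31)]. For example, equally spaced means at r = 0.5 give 9.375/(0.75 × 1.0323) = 12.11.

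**95% half-width of a pairwise difference.** Unadjusted: 2.0345 × 12 × √(2/12) = 9.97 cm². Adjusted: 2.0369 × 12 × √(1 − r²) × √[(2/12)(1 + 1/31)].

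| | Unadjusted | r = 0 | r = 0.3 | r = 0.5 | r = 0.7 |
|---|---|---|---|---|---|
| Power, 62/54.5/47 | 74.8% | 73.2% | 77.4% | 85.3% | 95.9% |
| Power, 62/62/47 | 86.5% | 85.3% | 88.6% | 93.9% | 99.0% |
| Half-width, cm² | 9.97 | 10.14 | 9.67 | 8.78 | 7.24 |

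Power breaks even at r of about 0.18. With equally spaced means, r of about 0.38 brings power to 80%. At r = 0.5 the gain is equivalent to 36/(0.75 × 1.0323) = 46.5, or about 46 participants.

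**Simulation check.** With 40,000 trials per setting, adjusted power was 73.3%, 77.5%, 85.2% and 96.0% for equally spaced means. Type I error was 4.8% to 5.1% for both tests.

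**Noisier training values.** Let s be the stable share of the Visit 2 variance, and c the Visit 1 noise variance relative to Visit 2. Then r = s/√[s + c(1 − s)]. With c = 2:

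| s | r | Adjusted power, 62/54.5/47 | Half-width, cm² |
|---|---|---|---|
| 0.3 | 0.23 | 75.7% | 9.87 |
| 0.5 | 0.41 | 81.2% | 9.26 |
| 0.7 | 0.61 | 91.3% | 8.00 |

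At s = 0.3, c has to reach about 3.3 before r falls to break-even.

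**The case against.** The strongest reply is that nothing is wrong. The ANOVA is valid and the stated group size reproduces. Unadjusted power falls below 80% only under the equally spaced pattern, which the plan does not name. All of that stands, and it is why the point concerns efficiency only.

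Second, the covariate is not collected in the plan, and its value depends on an unknown r. At r = 0.3 the gain is only 2 to 3 power points, and below about 0.18 adjustment loses power. This also stands: the documents cannot show on which side of break-even this trial lies.

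Third, Visit 1 values are taken while participants are still learning. The protocol itself says: "We have found this training session significantly reduces anxiety and variability in pain and hypersensitivity ratings on subsequent study days". That argues for a weaker covariate. The calculation with doubled Visit 1 noise variance shows a smaller gain, under 1 point at s = 0.3, but not a loss.

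Fourth, the sessions are not identical. Visit 1 has no lumbar puncture. An occlusive dressing is mentioned only at Visit 1, and the same leg or site is not specified. Such differences may lower r. A shift between visits common to all groups does not bias the randomized comparison.

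Fifth, the effect may be proportional, with the SD shrinking along with the mean. Simulated under that assumption, unadjusted power is about 85% (equally spaced) or 93% (one group differs), and adjustment at r = 0.5 adds about 4 to 8 points. The case for adjusting is then weaker but remains.

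**Conclusion.** The point holds as an improvement worth making, not as a flaw in validity. The plan runs a session before randomization that could yield a pre-treatment value of its primary outcome, but neither requires that value nor uses it.

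The trade is uneven: about 1 to 2 power points lost if r is near 0, against 2 to 3 gained at r = 0.3 and about 7 to 10 at r = 0.5. These sizes assume an SD of 12 cm², 12 per group, an additive effect of 15 cm² with constant SD, and an r that the documents do not supply. Confidence in the structure of the argument is high. Confidence in the size of the gain is moderate, because it depends on r.

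**What to change.** - Under Study Visit 1, add that the area of hyperalgesia is mapped and recorded after the first rekindling, by the same method as at Visit 2.
- Under Group comparison, prespecify ANCOVA as the primary analysis: Visit 2 area after the first rekindling as outcome, group as factor, Visit 1 area as the only covariate.
- State before unblinding how a missing Visit 1 area is handled, so that no participant drops out of the primary analysis for that reason.
- Keep the unadjusted one-way ANOVA as a prespecified sensitivity analysis.

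The cost is one standardised mapping and recording step per participant at a session already held, a few sentences of text, one error degree of freedom, and the small power loss if r proves to be near 0. No visits or participants are added.

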1. Male or female \geq 18 and $<$ 60 years of age, Body Mass Index (BMI) less than 40.
2. Generally in good health as determined by the Principal Investigator based on prior medical history, American Society of Anesthesiologists physical status 1 or 2.
3. Normal blood pressure (systolic 90-140 mmHg; diastolic 50-90 mmHg) resting heart rate 45-100 beats per minute) without medication.
4. Female subjects of child-bearing potential and those $<$ 1 year post-menopausal, must be practicing highly effective methods of birth control such as hormonal methods (e.g., combined oral, implantable, injectable, or transdermal contraceptives), double barrier methods (e.g., condoms, sponge, diaphragm, or vaginal ring plus spermicidal jellies or cream), or total abstinence from heterosexual intercourse for a minimum of 1 full cycle before study drug administration.

Exclusion Criteria:

1. Hypersensitivity, allergy, or significant reaction to any ingredient of the study drug, lidocaine or chili peppers.
2. Any disease, diagnosis, or condition (medical or surgical) that, in the opinion of the Principal Investigator, would place the subject at increased risk (active gynecologic disease in which increased tone would be detrimental e.g., uterine fibroids with ongoing bleeding), compromise the subject's compliance with study procedures, or compromise the quality of the data.
3. Women who are pregnant (positive result for serum pregnancy test at screening visit), women who are currently nursing or lactating, or those who have delivered within 2 years.
4. Currently taking prescription or over the counter pain medications (opioid or non-opioid), diuretics, blood pressure medication, heart medication or any other medication at the discretion of the investigators that would place the subject at increased risk.

RANDOMIZATION GROUPS

A computer generated randomization will be used to determine the group for each subject. Subjects will be randomized to receive an intrathecal injection of the saline placebo or one of two doses oxytocin.

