This Phase II trial will be performed with a data safety monitoring committee ([name] and [name].) who is not involved in the study. Data and adverse events will be reported to these individuals quarterly. Adverse events will also be reported to the IRB and the FDA (since trials are being conducted under an IND). Serious adverse events will be reported to all of these groups and the data safety monitoring individuals within 24 hr and the trials halted until feedback is obtained from each. Data and any adverse events will be monitored and reviewed by the PI after treatment of each subject.

Minority, Gender, and Children Participation

Based on previous experience with volunteer studies, women will represent 40-60% of participants in the proposed studies. However, as seen in the table below from the past cycle with volunteers, it is unlikely that more than 20% of participants will be minorities. There is no reason to suspect a difference among races in response to these analgesic compounds, so from a scientific viewpoint this will not be detrimental. We will recruit from our IRB approved Database (BG 05-468). Children under age 18 are not included in these protocols because this protocol involves the use of experimental compounds and we believe they should be first characterized in adults. Furthermore, the study of experimental pain in children volunteers is

difficult ethically. For these reasons we anticipate studying approximately 6-7% of our subjects under age 21, and none under age 18.

Volunteer Payment

Participants will be paid a total of \$500. We believe that this payment schedule is fair and appropriate, paying for each procedure attempted and an additional payment for completion of the entire study.

Placement of IV: \$25

If IV placement unsuccessful, the volunteer is paid and the study abandoned.

Placement of Spinal: \$125 and study drug administration

If the 1st spinal is attempted but proves unsuccessful, the volunteer is paid \$100 and the study abandoned,

Application of capsaicin cream: \$25 for each application (total \$50)

Completion of entire study: \$300

Volunteer must complete all of the above phases to receive this payment.

Long-term Follow-up

Volunteers will be contacted daily for 5 days, weekly for 1 month, and at 6 months after the study and questioned about neurologic symptoms, symptoms of post-dural puncture headache (spinal headache) or other complaints.

STATISTICAL RATIONALE

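### Optional improvement: equal numbers of men and women are planned, but neither the stated randomization nor the valid one-way ANOVA uses sex; stratifying by sex and adding a sex term together would cost about 0.1 power point

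*Combined protocol and SAP*

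**What the plan says.** The METHODS paragraph of the protocol opens with a recruitment aim: "Equal numbers of healthy men and women will be recruited". It does not say whether this balance is to hold within each of the three groups of 12.

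Under RANDOMIZATION GROUPS, allocation is described in two sentences. The first is "A computer generated randomization will be used to determine the group for each subject"; the second names the treatments. No stratification factor or block structure is given.

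The replacement rule in METHODS is that, after a failed intravenous or spinal placement, the team will "schedule another participant to receive the same randomization". The sex of the replacement is not mentioned. Up to 40 people may be enrolled to obtain 36 evaluable.

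Under STATISTICAL RATIONALE the endpoint is fixed: "Primary outcome measure will be the area of hyperalgesia after the first skin heating following topical capsaicin". Areas "will be compared among the three groups using one-way ANOVA". Sex does not appear in that section.

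Under Minority, Gender, and Children Participation, the forecast is that "women will represent 40-60% of participants in the proposed studies".

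**The concern.** Sex is known before randomization and is already a recruitment target. A baseline factor of that kind can be used to remove variance from the error term if it is related to the outcome. Here it is controlled at recruitment and then not used, either in the stated allocation or in the analysis.

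Precision is what is at stake. With 36 evaluable subjects there is little to spare: the planned three-group F test has power 0.748 for a 15 cm² range when the third mean lies midway. If men and women differ in area of hyperalgesia, that difference stays in the residual of the one-way ANOVA and lowers power below what the same 36 people could give.

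**Working it through.** **Inputs from the STATISTICAL RATIONALE and METHODS.** Placebo area 62 ± 12 cm² (the ± figure read as an SD), target difference 15 cm², 12 per group, three groups, α = 0.05, power 0.80. Two-sided testing is assumed for the two-group check. The documents give no sex effect, so the male-female difference *d* is an assumption, taken as 0, 3.6, 6 and 12 cm² (0, 0.3, 0.5 and 1 SD).

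**Step 1: the plan's own figure.** A two-sample t-test with SD 12 and difference 15 has power 79.6% at 11 per group and 83.3% at 12. So 12 is the smallest group size reaching 80%, and the stated size is reproduced as a two-group calculation.

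**Step 2: the planned three-group F test.** The noncentrality is λ = 12 × Σ(μᵢ − μ̄)² / σ², with 2 and 33 df.
- Third mean midway (62, 54.5, 47): Σ = 7.5² + 0 + 7.5² = 112.5; λ = 12 × 112.5 / 144 = 9.375; power 0.748.
- One group differs (62, 62, 47): Σ = 5² + 5² + 10² = 150; λ = 12 × 150 / 144 = 12.5; power 0.865.

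**Step 3: group + sex, list stratified, 6 men and 6 women per group.** With a total within-group SD of 12 and equal numbers of each sex, sex accounts for d²/4 of the variance. The residual variance is 144 − d²/4, and the error df falls from 33 to 32.

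| Assumed d (cm²) | Residual variance | λ, midway | Power, midway | λ, one differs | Power, one differs |
|---|---|---|---|---|---|
| 0 | 144 | 9.375 | 0.747 | 12.5 | 0.864 |
| 3.6 | 140.76 | 9.59 | 0.757 | 12.79 | 0.872 |
| 6 | 135 | 10.0 | 0.775 | 13.33 | 0.886 |
| 12 | 108 | 12.5 | 0.864 | 16.67 | 0.946 |

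Break-even, where the lost degree of freedom is just repaid, is at a variance share of about 0.003, so d = 2 × 12 × √0.0029 ≈ 1.3 cm² (0.11 SD).

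**Step 4: the sex term without stratification.** Averaged exactly over all allocations of 18 women to three groups of 12, power for d = 0, 6, 12 is 0.733, 0.762, 0.853 (midway) and 0.853, 0.876, 0.939 (one differs). If sex has no effect, the loss against the plan is 0.748 − 0.733 = 1.5 points or 0.865 − 0.853 = 1.2 points. Break-even moves to about 4.3 cm² (0.36 SD). The reason is chance imbalance: an unstratified list gives exactly 6 women in every group only about 9% of the time.

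**Step 5: stratification without the sex term.** Simulated type I error of the one-way ANOVA (100,000 trials per setting) is 0.042 at d = 6 and 0.019 at d = 12. With the sex term included it is 0.051 and 0.050. For an unstratified list and the planned ANOVA it is 0.050 to 0.051 throughout.

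**Step 6: unequal totals.** 40-60% of 36 is 14.4 to 21.6, so 15 to 21 women. With 15 or 21 women (5 or 7 per group) the residual variance is 144 − d² × (15/36) × (21/36). Power for d = 0, 6, 12 is then 0.747, 0.774, 0.861 (midway) and 0.864, 0.886, 0.944 (one differs), within 0.3 points of the equal split.

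**The case against.** The best reply is that nothing is broken. A one-way ANOVA on randomized groups is a legitimate primary analysis, and an aim to recruit equal numbers promises neither stratification nor adjustment. That stands, and it is why this is only a suggestion. A reader might infer that leaving sex out biases the comparison or inflates the error rate. It does neither: randomization protects the comparison on average, and the error term already allows for chance imbalance in sex.

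The benefit also rests on a number that the documents do not contain. At 0.3 SD or less the gain is under 1 point, and 8 to 12 points needs a full 1 SD difference between men and women, for which the documents offer no support. This stands too. The case for the change is that its cost is small, not that its gain is known.

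The low cost holds only for the two changes made together (Step 4). The warning against stratifying alone should not be overstated either: the test becomes conservative under the null, but simulated power at the 15 cm² target does not fall. It is about 0.75 at either 6 or 12 cm² with the midway pattern, against 0.748 planned.

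A reader might also see a contradiction between equal numbers in METHODS and the 40-60% forecast for women. There is none: 50% lies inside that range, the forecast is drawn from earlier volunteer studies, and the model works with either.

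Finally, the randomization text is a short summary, so stratification may have been used without being reported. The documents cannot settle that.

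**Conclusion.** The point holds as a cheap, optional improvement and not as an error. Stratifying by sex and adjusting for it would lose about 0.1 power point if sex is unrelated to the area of hyperalgesia. It would gain 0.7 to 0.9 points at a 3.6 cm² sex difference, 2 to 3 points at 6 cm², and 8 to 12 points at 12 cm².

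These figures assume that 12 is a within-group SD including any sex difference, that the sex effect is the same in every group, that 36 subjects are evaluable, and that the sex split is near-equal across groups. Every sex effect shown is an assumption. The point should rank below any finding of an actual defect.

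**What to change.** Before unblinding, and preferably before enrolment:

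1. Make the primary analysis an ANOVA of area of hyperalgesia on group and sex, testing group with 2 and 32 df.
2. Stratify the computer-generated list by sex, with permuted blocks within each sex. If this was already done, say so under RANDOMIZATION GROUPS.
3. Let a replacement for a failed placement come from the same sex stratum. At most 4 people are affected (40 − 36), so this is minor.

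Items 1 and 2 belong together. If the list can no longer be stratified, the sex term alone is a closer call: it pays only if the sex difference exceeds about 4.3 cm², and keeping the planned ANOVA is then reasonable. If the list is already stratified, the sex term should be added so that the test keeps its nominal level.

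The cost is one model term, two lists instead of one, one error degree of freedom, and possibly some waiting late in enrolment for a participant of the needed sex. The sample size does not change, and exact 6/6 balance is not required.
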